## **18. Special Reporting Situations**

SAE's include death, life threatening adverse experiences, hospitalization or prolongation of hospitalization, disability or incapacitation, overdose, congenital anomalies and any other serious events that may jeopardize the subject or require medical or surgical intervention to prevent one of the outcomes listed in this definition.

Reporting of SAE to IRB

- All SAEs occurring on this study will be reported to the IRB according to the IRB policy, which can be accessed via the following link:  
[https://research.weill.cornell.edu/sites/default/files/immediate\\_reporting\\_policy.pdf](https://research.weill.cornell.edu/sites/default/files/immediate_reporting_policy.pdf)

Reporting of SAE to FDA [For protocols where WCMC is the Sponsor-Investigator]

- If an SAE occurs on this study, the event will be filed on a MedWatch form with the FDA. The investigator must notify the FDA of any SAE's as soon as possible but no later than 7 calendar days after the initial receipt of the information

Safety events of interest for a Janssen medicinal product that require expediting reporting and/or safety evaluation include, but are not limited to:

- Drug exposure during pregnancy (maternal and paternal)
- Overdose of a Janssen medicinal product
- Exposure to a Janssen medicinal product from breastfeeding
- Suspected abuse/misuse of a Janssen medicinal product
- Inadvertent or accidental exposure to a Janssen medicinal product
- Any failure of expected pharmacological action (i.e., lack of effect) of a Janssen medicinal product
- Medication error involving a Janssen medicinal product (with or without patient exposure to the Janssen medicinal product, e.g., name confusion)
- Suspected transmission of any infectious agent via administration of a medicinal product
- Unexpected therapeutic or clinical benefit from use of a Janssen medicinal product

**These safety events may not meet the definition of an adverse event; however, from a Janssen Scientific Affairs, LLC perspective, they are treated in the same manner as adverse events. Special situations should be recorded on the Adverse Event page of the CRF.**

Any special situation that meets the criteria of a serious adverse event should be recorded on a Serious Adverse Event Report Form and be reported to Janssen Scientific Affairs, LLC **within 24 hours of becoming aware of the event.**

### **18.1.Pregnancy**

All initial reports of pregnancy must be reported to Janssen Scientific Affairs, LLC by the PRINCIPAL INVESTIGATOR **within 24 hours of becoming aware of the event** using the Serious Adverse Event Form. Abnormal pregnancy outcomes (e.g. spontaneous abortion, fetal death, stillbirth, congenital anomaly, ectopic pregnancy) are considered serious adverse events and must be reported using the Serious Adverse Event Form.

Any subject who becomes pregnant during the study must be promptly withdrawn from the study and discontinue further study treatment.

Because the effect of the Janssen medicinal product on sperm is unknown, pregnancies in partners of male subjects exposed to a Janssen medicinal product will be reported by the PRINCIPAL INVESTIGATOR within 24 hours of their knowledge of the event using the Serious Adverse Event Form. Depending on local legislation this may require prior consent of the partner.

Follow-up information regarding the outcome of the pregnancy and any postnatal sequelae in the infant will be required.

## **19. Maintenance of Safety Information**

All safety data should be maintained in a clinical database in a retrievable format. The PRINCIPAL INVESTIGATOR shall provide all adverse events, both serious and non-serious, in report format. However, in certain circumstances more frequent provision of safety data may be necessary, e.g. to fulfill a regulatory request, and as such the data shall be made available within a reasonable timeframe at Janssen Scientific Affairs, LLC request.

## **20. Procedures for Reporting Safety Data and Product Quality Complaints for Janssen Medicinal Products to Janssen Scientific Affairs, LLC**

All adverse events and special situations, whether serious or non-serious, related or not related, following exposure to a Janssen medicinal product are to be documented by the investigator and recorded in the CRF and in the subject's source records. Investigators must record in the CRF their opinion concerning the relationship of the adverse event to a Janssen medicinal product.

All (serious and non-serious) adverse events reported for a Janssen medicinal product should be followed-up in accordance with clinical practice.

### **20.1.SAEs, Adverse Events of Special Interest and Special Reporting Situations**

All serious adverse events that have not resolved by the end of the study, or that have not resolved upon discontinuation of the subject's participation in the study, must be followed until any of the following occurs:

- The event resolves
- The event stabilizes
- The event returns to baseline, if a baseline value/status is available
- The event can be attributed to agents other than the study drug or to factors unrelated to study conduct
- It becomes unlikely that any additional information can be obtained (subject or health care practitioner refusal to provide additional information, lost to follow-up after demonstration of due diligence with follow-up efforts)

The PRINCIPAL INVESTIGATOR will transmit all SAEs, Adverse Events of Special Interest and special situations following exposure to a Janssen product under study in a form provided by Janssen Scientific Affairs, LLC in accordance with Section 15, Transmission Methods, in English within 24-hours of becoming aware of the event(s).

In the event the study is blinded, the PRINCIPAL INVESTIGATOR will submit an unblinded SAE, Adverse Events of Special Interest or pregnancy exposure report to Janssen Scientific Affairs, LLC.

All follow-up information for serious adverse events that are not resolved at the end of the study or by the time of patient withdrawal must be reported directly by the PRINCIPAL INVESTIGATOR, within 24 hours becoming aware, to Janssen Scientific Affairs, LLC using the Janssen Scientific Affairs, LLC Serious Adverse Event Report

All available clinical information relevant to the evaluation of a related SAE, serious ADR or special situation is required.

## **20.2. Non-Serious AEs**

All non-serious adverse events should be reported to Janssen Scientific Affairs, LLC according to the timeframe outlined in the Research Funding Agreement section entitled Reporting of Data.

## **20.3. PQC Reporting**

A PQC may have an impact on the safety and efficacy of the product. Timely, accurate, and complete reporting and analysis of PQC information from studies are crucial for the protection of patients, investigators, and Janssen Scientific Affairs, LLC, and are mandated by regulatory agencies worldwide. Janssen Scientific Affairs, LLC has established procedures in conformity with regulatory requirements worldwide to ensure appropriate reporting of PQC information. Lot and/or Batch #s shall be collected for any reports failure of expected pharmacological action (i.e., lack of effect). The product should be quarantined immediately and if possible, take a picture.

All initial PQCs involving a Janssen medicinal product under study must be reported to Janssen Scientific Affairs, LLC by the PRINCIPAL INVESTIGATOR within 24 hours after being made aware of the event. The Janssen contact will provide additional information/form to be completed.

If the defect for a Janssen medicinal product under study is combined with either a serious adverse event or non-serious adverse event, the PRINCIPAL INVESTIGATOR must report the PQC to Janssen Scientific Affairs, LLC according to the serious adverse event reporting timelines. A sample of the suspected product should be maintained for further investigation if requested by Janssen Scientific Affairs, LLC.

## **21. Transmission Methods**

The following methods are acceptable for transmission of safety information to Janssen Scientific Affairs, LLC:

- Electronically via Janssen SECURE Email service (preferred)
- For business continuity purposes, if SECURE Email is non-functional:
  - Facsimile (fax), receipt of which is evidenced in a successful fax transmission report
- Telephone (if fax is non-functional).

Please use the contact information and process information provided by Janssen Scientific Affairs, LLC.

## **22. Data and Safety Monitoring Plan (DSMP)**

Monitoring activities will be commensurate with the nature, size and complexity of the trial in accordance with institutional policies and will be determined after IRB and Data Safety Monitoring Board (DSMB) review of the protocol immediately prior to study activation. For this study we will utilize a Weill Cornell Medicine DSMB.

We will evaluate safety of combination therapy after 12 subjects have been enrolled onto the protocol and completed 8 weeks of combination induction therapy. The study team will review all subject data at this specified time point and provide a written report to the DSMB for review. Stopping rules will be employed in this study based on observed toxicities from monotherapy trials in subjects with multiple myeloma receiving daratumumab or WM subjects receiving monotherapy ibrutinib. For purposes of this safety analysis, each subject will be assessed individually and toxicities tabulated. Only toxicities occurring within the first 8 weeks of combination treatment will be considered for potential study termination.

In monotherapy daratumumab or ibrutinib studies, Grade 3 or greater non hematologic toxicities were rare with the most common event being pneumonia noted in 6% of subjects respectively for daratumumab and ibrutinib (data from prescribing inserts). Grade 3 or greater hematologic toxicities when restricted to anemia, thrombocytopenia, or neutropenia were noted in up to 20% of subjects treated with daratumumab monotherapy and up to 19% in subjects treated with ibrutinib monotherapy.

Based on these observed events we will stop the study if 5 of the first 12 subjects enrolled experience a Grade 3 or greater, toxicity (heme or non-heme) which leads to a study drug hold greater than 28 days or leads to either study drug discontinuation within the first two months of treatment. Any drug hold that occurs within the first 8 weeks but extends beyond the initial 8 week monitoring period will be followed for a full 28 days. For a toxicity to be included in this analysis, the toxicity must be considered due to the study drug per investigator assessment. Accrual will be held upon enrollment of the 12th evaluable subject until they have been observed through induction and the study team in consultation with the DSMB have made a determination regarding additional enrollment, this study hold is anticipated to last approximately 3 months.

- Type, severity, frequency, duration, and relationship to study drug of any AEs or abnormalities of laboratory tests, SAEs, or AEs leading to discontinuation will be recorded.
- Monthly IgM serum levels and every 6 month CT scans will be recorded and used to assess efficacy.
- Subjects may be discontinued at any time at the discretion of the Investigator. The following may be justifiable reasons for the Investigator to remove a subject from the study:
  - Non-compliance
  - Withdrawal of consent by the subject
  - Erroneous inclusion into the study
  - Development of defined exclusion criteria
  - Intolerable toxicity or adverse event
  - Pregnancy
  - Termination of the study by the sponsor

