#### **Treatment Phases:**

Treatment will consist of induction, continuation, and maintenance phases. Induction will be defined as the first 2 cycles of combination treatment. The consolidation phase will include treatment with daratumumab on day 1 and day 15 of each cycle starting with cycle 3 through cycle 6. Starting at cycle 7 subjects will enter the maintenance phase with monthly daratumumab infusions until Cycle 24 day 1 (two years) at which point they will complete their combination treatment with daratumumab. Cycle 25 and beyond patients will continue on ibrutinib monotherapy.

Subjects will have doctor visits on each day of treatment with daratumumab but required study visits will only occur monthly for the first year followed by every 3 cycles for the remainder of the study. On non-study visits during induction, subjects will have baseline labwork considered to be standard of care obtained at the discretion of the investigator followed by daratumumab infusions. Subjects will take three, 140mg capsules of ibrutinib orally, daily starting on the same day as infusion and continue daily through all cycles.

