arm. In total 31 patients were accrued to the ibrutinib only arm between August 2014 and February 2015. Thirteen (42%) of the 31 patients had high-risk disease per the International Prognostic Scoring System Waldenström Macroglobulinemia. At a median follow-up of 18.1 months, the overall response rate was 90% with 71% of patients attaining a major response. The estimated 18 month PFS was 86% and the 18 month OS was 97%. Baseline hemoglobin of 10.3 g/dL increased to 11.4 g/dL after 4 weeks of treatment. Grade 3 or greater adverse events were neutropenia (13%), hypertension (10%), and anemia, thrombocytopenia, and diarrhea (6%) each. Serious adverse events occurred in 10 patients (32%) and most often related to infections. Five patients discontinued ibrutinib; 3 due to progression and 2 due to adverse events.

Given the results of the Phase II data the Federal Drug Administration (FDA) gave accelerated approval for the treatment of patients in both treatment naïve and relapsed refractory settings.

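### The only numeric stopping rule covers the first 12 subjects and toxicity arising in the first 8 weeks of combination; no stated rule covers subjects 13-24 or later toxicity

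*Combined protocol and SAP*

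**What the plan says.** Section 22 plans one formal safety review: "We will evaluate safety of combination therapy after 12 subjects have been enrolled onto the protocol and completed 8 weeks of combination induction therapy". The boundary at that review is "we will stop the study if 5 of the first 12 subjects enrolled experience a Grade 3 or greater, toxicity (heme or non-heme"), where the toxicity must be one "which leads to a study drug hold greater than 28 days or leads to either study drug discontinuation within the first two months of treatment". Three qualifiers apply.

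- Attribution: "the toxicity must be considered due to the study drug per investigator assessment".
- Holds: "Any drug hold that occurs within the first 8 weeks but extends beyond the initial 8 week monitoring period will be followed for a full", the period being 28 days. Follow-up of a hold can therefore pass week 8, but its onset cannot.
- Window: "Only toxicities occurring within the first 8 weeks of combination treatment will be considered for potential study termination".

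Accrual is held at the 12th evaluable subject while the study team and the DSMB decide on further enrolment. Neither Section 16 nor Section 22 gives a second look, a boundary for subjects 13-24 or a boundary for later toxicity. Section 22 also lists termination by the sponsor, but only among the reasons for removing a subject, and without a criterion.

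Combination treatment runs far beyond the window. The synopsis says: "Starting at cycle 7 subjects will enter the maintenance phase with monthly daratumumab infusions until Cycle 24 day 1 (two years").

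**The concern.** Safety and toxicity form the only primary objective (Section 1.1), and Section 6.2.5 reports no clinical studies of daratumumab in Waldenström's macroglobulinemia. The protocol expects risk beyond week 8. Section 3 refers to toxicity from long-term continuous therapy. Table 1, footnote d, schedules HBV DNA testing for at-risk subjects to Cycle 31. Section 17.4 requires new malignancies to be reported throughout treatment and follow-up. These data are collected, but the stated basis for terminating the study does not use them.

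The second half of enrolment has no boundary at all. The first 12 subjects are also not split by cohort. Cohort A starts ibrutinib on study, while Cohort B has already taken it for at least 6 months and is selected for having no ongoing non-hematologic ibrutinib toxicity above Grade 1. One of these two populations could be thinly represented at the only look.

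**Working it through.** **The plan's own figure.** The stopping rule has no stated operating characteristics. The one computed design figure is the Clopper-Pearson interval in Section 16. With n = 12 and x = 0.15 × 12 = 1.8 it reproduces as 1.57% to 46.54%, width 44.97%, against the stated 1.6% to 46.5%, width 45.0%. It does not bear on the rule's coverage.

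**Coverage.** Inputs: 24 subjects (synopsis), 24 combination cycles (Section 9.3.4), 28-day cycles (Section 12.1), and a rule limited to 12 subjects and 8 weeks (Section 22).

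- By patient-weeks: (12 × 8) / (24 × 24 × 4) = 96 / 2,304 = 4.2%.
- With two years taken as 104 weeks: 96 / (24 × 104) = 3.8%.
- Section 9.3 gives maintenance as 23 cycles, whereas Section 9.3.3 gives Cycles 7-24, which is 18; these must be reconciled. At 2 + 4 + 23 = 29 combination cycles, the share is (12 × 2) / (24 × 29) = 3.4%.
- By planned infusions, at 8 + 8 + 18 = 34 per subject: (12 × 8) / (24 × 34) = 96 / 816 = 11.8%. This is higher because dosing is front-loaded.

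**Current rule.** Let p be the true probability that a subject has a qualifying event, with subjects independent. The documents give no value for p, so a range is shown. The probability of stopping is a = P(Bin(12, p) ≥ 5). The probability that subjects 13-24 reach 5 of 12 when the first 12 did not, so that nothing is triggered, is a(1 − a).

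| p | a | a(1 − a) |
|---|---|---|
| 15% | 2.4% | 2.3% |
| 20% | 7.3% | 6.7% |
| 30% | 27.6% | 20.0% |
| 40% | 56.2% | 24.6% |

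At p = 40% the only look is passed 100 − 56.2 = 43.8% of the time, and no rule applies afterwards.

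**Halting at the fifth event.** Five or more events occur among the first 12 exactly when a fifth event occurs at or before subject 12. Acting at that event therefore leaves a unchanged. The mean subject number at which the boundary is met, capped at 12, is 11.96 at p = 15%, 11.4 at 30%, 10.6 at 40% and 8.2 at 60%. The saving in subjects is small unless toxicity is very frequent.

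**Extending the same 8-week event to all 24.** For 5/12 kept and 8/24 added:

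P(stop) = a + Σ (k = 0 to 4) P(Bin(12, p) = k) × P(Bin(12, p) ≥ 8 − k)

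| p | 5/12 now | 5/12 plus 8/24 | 8/24 alone | 5/24 |
|---|---|---|---|---|
| 15% | 2.4% | 2.4 + 1.2 = 3.6% | 2.0% | 28.7% |
| 20% | 7.3% | 7.3 + 5.1 = 12.3%* | 8.9% | 54.0% |
| 30% | 27.6% | 27.6 + 20.6 = 48% | 43.5% | 89% |
| 40% | 56.2% | 56.2 + 26.9 = 83% | 80.8% | 99% |

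*Terms rounded separately.

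Even with all 24 subjects covered, an 8-week event reaches (24 × 8) / 2,304 = 192 / 2,304 = 8.3% of patient-weeks. Later toxicity would still depend on periodic review.

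**The case against.** The strongest reply is that the sentence on the 8-week window directly follows one introducing the 12-subject safety analysis, so it may only define what counts at that look. A reader might infer that the DSMB is forbidden to act on later toxicity. The documents do not support that. Section 22 leaves monitoring activities to be settled after IRB and DSMB review under institutional policy, and it mentions sponsor termination with no time limit. What is established is that no later numeric rule exists and that the sentence, read literally, excludes later events.

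A reader might also infer that late toxicity goes unwatched. It does not: there are per-patient hold and discontinuation rules (Section 12.4), HBV monitoring, 24-hour reporting of events of special interest (Sections 17.3 and 17.4) and SAE reports to the IRB and FDA (Section 18). These act on individual subjects or report single events; none states how accumulating events lead to a study-level decision.

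A third tempting reading is that enrolment must run to subject 12 even after an early fifth event. The text does not say so; the accrual hold at subject 12 is a separate provision, so this is ambiguity. The gain from clarifying it is also limited by ascertainment. With 24 subjects planned over 2 years, or about one a month, 8 weeks plus a 28-day hold lets in roughly three more.

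The 4.2% figure assumes that every subject completes 24 cycles, and the infusion-based 11.8% is kinder to the plan. Finally, the published ibrutinib-alone result in Section 6.1.5, "Serious adverse events occurred in 10 patients (32%) and most often related to infections", gives no onset times and is not evidence of late toxicity.

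**Conclusion.** The point stands as a gap in the stated rule. The only numeric boundary covers half the subjects and 3.4% to 4.2% of planned combination patient-time (11.8% of planned infusions), and its wording leaves later toxicity out of the stated grounds for termination. It does not show that the DSMB is powerless or that subjects go unmonitored. The coverage shares assume full completion; early withdrawal would raise them. The stopping probabilities assume a constant, independent event rate, which the documents do not supply.

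Carrying the count of 5 over to 24 subjects is a tempting remedy, but it would halve the tolerated proportion from 42% (5/12) to 21% (5/24) and raise the stopping probability at a true rate of 15% from 2.4% to 28.7%. Nothing in the documents justifies that. The change recommended is a low-cost improvement to a viable pilot.

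**What to change.** In Section 22:

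1. Limit the 8-week sentence to the 12-subject look. State that drug-related events after week 8, and events in subjects 13-24, can also lead to a DSMB recommendation to pause or terminate. Support this with cumulative toxicity tables by cohort, sent to the existing DSMB at regular intervals (for example every 6 months) until the last subject ends daratumumab.
2. State that accrual halts when the fifth qualifying event occurs. The probability of stopping under 5/12 does not change.
3. If a numeric boundary is extended to all 24 subjects on the same 8-week event, choose it from a table of operating characteristics such as the one above, against an event rate the sponsor declares acceptable. Keeping 5/12 and adding 8/24 is one candidate; 5/24 should not be adopted by default.
4. In the same edit, reconcile enrolled with evaluable for the first 12, and the first 8 weeks of combination with the first two months of treatment. The latter two differ for Cohort A because of its one-cycle ibrutinib lead-in.

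The cost is a wording change and short periodic reports to a DSMB already in place, with no added subjects, visits or data collection. If 8/24 is added, the chance of an unnecessary pause rises modestly, from 2.4% to 3.6% at a true rate of 15% and from 7.3% to 12.3% at 20%.

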#### **12.4. Dose Delays and Dose Modification**

Dose modification of daratumumab is not permitted, but dose delay remains the primary method for managing daratumumab-related toxicities. Ibrutinib and daratumumab therapy should be held until recovery upon the onset of any of the following toxicities:

- Grade 4 hematologic toxicity
- Grade 3 thrombocytopenia with bleeding
- Febrile neutropenia of any grade
- Grade 3 or higher nonhematologic toxicities with the following exceptions:
  - Grade 3 nausea that responds to anti-emetics within 7 days
  - Grade 3 vomiting that responds to anti-emetics within 7 days
  - Grade 3 diarrhea that responds to anti-diarrheal within 7 days
  - Grade 3 fatigue that was present at baseline or that lasts for <7 days.
  - Grade 3 asthenia that was present at baseline or that lasts for less than 7 days after.

Supportive care should be provided, and growth factor support should be applied as outlined in

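### Section 22's only numerical stop counts a drug-related death as at most one of five events, and the protocol does not require DSMB review or an enrolment pause because of a death before the hold at the 12th subject

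*Combined protocol and SAP*

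**What the plan says.** All study-level stopping text is in Section 22 of the combined protocol and SAP. The rule is "we will stop the study if 5 of the first 12 subjects enrolled experience a Grade 3 or greater, toxicity (heme or non-heme", and the toxicity must also cause a drug hold of more than 28 days or discontinuation of either drug within two months. Two further limits apply: "Only toxicities occurring within the first 8 weeks of combination treatment will be considered for potential study termination", and "the toxicity must be considered due to the study drug per investigator assessment". Death is not named.

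The scheduled safety look follows completion of the 8-week induction by 12 subjects, when the study team reports all subject data to the DSMB. Enrolment stops at that point whatever the event count: "Accrual will be held upon enrollment of the 12th evaluable subject until they have been observed through induction", and "this study hold is anticipated to last approximately 3 months".

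Other safeguards:

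- Section 17.7 makes every death a serious adverse event. Section 18 sends it to the IRB under its policy and to the FDA within 7 calendar days. Section 20.1 sends it within 24 hours to the company that supplies daratumumab.
- Sections 12.2 and 12.4 act on the individual patient, for example "Ibrutinib and daratumumab therapy should be held until recovery upon the onset of any of the following toxicities".
- Section 22 lists "Termination of the study by the sponsor" among the reasons for removing a subject.
- Section 22 says that monitoring will be "in accordance with institutional policies and will be determined after IRB and Data Safety Monitoring Board (DSMB) review of the protocol".

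**The concern.** Safety is the primary objective (Section 1.1), and Section 6.2.5 states that daratumumab had not been studied clinically in this disease. One would expect a death attributed to the combination to prompt an independent look before more patients start treatment. Under the written rule it has no more weight than a Grade 3 toxicity with a five-week drug hold. It does not count at all if it occurs after week 8 of combination treatment or in subjects 13 to 24. The expedited reports go to the IRB, the FDA and the company, and no text sends them to the DSMB or ties them to enrolment. At stake is how many patients start the combination between an early related death and the first DSMB review that the protocol requires.

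**Working it through.** **1. The plan's own figure.** The plan gives no operating characteristics for the 5-of-12 rule. Its one computed design figure is the exact 95% interval in Section 16 for 12 patients at a 15% toxicity rate. With x = 0.15 × 12 = 1.8, the Clopper-Pearson limits are the 2.5% point of Beta(1.8, 11.2) = 1.57% and the 97.5% point of Beta(2.8, 10.2) = 46.54%, which reproduces the stated 1.6% to 46.5%.

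**2. What the rule tolerates.** Each subject counts once, so four drug-related deaths among the first 12 (33%; exact 95% interval 9.9% to 65.1%), with no other counted event, leave the rule unmet.

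**3. Subjects still to enrol after an early death.** The synopsis plans 24 subjects over 2 years, about one a month. Suppose subject 1 dies of a related cause:

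- Cohort B, week 1: 11 remain before the 12th.
- Cohort B, week 8: 10 remain.
- Cohort A, week 8 of combination (week 12 after enrolment, because of the 4-week lead-in): 9 remain.

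**4. Chance of at least one death in the first 12 inductions.** P = 1 − (1 − d)^12, where d is the 8-week death probability.

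The documents anchor d in two ways.

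- *Ibrutinib monotherapy, all causes, constant hazard assumed.* Two-year survival is 95.2% (Section 2), so the hazard is −ln(0.952)/2 = 0.0246 per year and d = 1 − exp(−0.0246 × 56/365.25) = 0.376%. Eighteen-month survival is 97% (Section 6.1.5), so the hazard is −ln(0.97)/1.5 = 0.0203 and d = 0.311%.
- *Daratumumab monotherapy in myeloma, related deaths (Section 6.2.7).* There were 14 deaths, given as 9%, so N is between 148 and 164, and none was judged related. The one-sided 95% upper limit, 1 − 0.05^(1/N), is 2.0% to 1.8%. This is an upper limit over a follow-up that is not stated, so 2% within 8 weeks is pessimistic against it.

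The rates of 1% and 2% below are assumptions. They are about 2.7 and 5.3 times the 0.376% all-cause figure.

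| 8-week death probability | P(at least 1 in 12) | P(5 or more deaths) |
|---|---|---|
| 0.311% (all causes) | 3.7% | below 0.001% |
| 0.376% (all causes) | 4.4% | below 0.001% |
| 1% (related, assumed) | 11.4% | below 0.001% |
| 2% (related, assumed) | 21.5% | 0.0002% |

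**5. Allowing for other counted toxicity.** Let a further proportion t of subjects have a non-fatal counted event. The rule stops with probability P(Binomial(12, d + t) ≥ 5). The chance of at least one death with the rule unmet is P(total < 5) − Σ(k = 0 to 4) C(12, k) t^k (1 − d − t)^(12 − k). Both values of t are assumptions, and in the 0.376% row every death is treated as counted.

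| d | Rule stops, t = 10% | Death, rule unmet, t = 10% | Rule stops, t = 20% | Death, rule unmet, t = 20% |
|---|---|---|---|---|
| 0.376% | 0.5% | 4.3% | 7.8% | 3.7% |
| 1% | 0.7% | 11.1% | 8.7% | 9.4% |
| 2% | 0.9% | 20.9% | 10.2% | 17.4% |

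If an early related death occurs, the numerical rule will usually not be what brings it to the DSMB.

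**6. How often a death trigger could fire.** An all-cause ceiling comes from 1 − exp(−hazard × person-years), with hazards 0.0203 and 0.0246. Up to the hold, 12 subjects entering monthly contribute 11 + 10 + … + 0 = 66 months = 5.5 person-years, giving 10.6% to 12.7%. Over full accrual, 24 subjects entering uniformly over 2 years contribute 24 person-years, giving 38.6% to 44.6%. Over the first 12 inductions alone it is the 3.7% to 4.4% of step 4.

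**The case against.** The strongest objection is that the gap may already be filled. Section 22 leaves monitoring to institutional policy and to IRB and DSMB review before activation, and a death trigger is an ordinary thing to find there. This stands as a limit. A reader might infer that the trial has no death trigger, or that a death would pass unseen, and the documents support neither. They show only that the protocol states no such trigger, while the expedited reports make any death visible within days to bodies that can act.

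Second, the size is modest. A reader might try 8-week related-death rates of 5% or 10%, which would make an early death close to an even chance or likely. Nothing in the documents supports such rates. The ibrutinib survival figures put all-cause 8-week mortality below 0.4%, and the daratumumab study reports no related deaths. The combination could be worse than either drug alone, but by how much is unknown.

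Third, an unmet rule is not itself harm. The hold at the 12th subject happens regardless, and the team then reports all data, not only counted events. The tables measure how rarely the numerical rule responds to a death; they do not count patients injured. This is correct.

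Fourth, the benefit is calculated over 8 weeks in 12 subjects, while a trigger that covers all of accrual has a much higher ceiling for firing. The comparison is fair, and the fix offers a narrower option. None of these objections points to text that requires the DSMB to look, or enrolment to pause, because of an early death.

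**Conclusion.** The point holds as an inexpensive improvement to a design choice. It is not an error in the plan's calculations. Followed as written, the protocol would allow about 9 to 11 further subjects to enrol after a related death in subject 1 before a DSMB review is required. The chance that any death occurs in the first 12 inductions is about 4% if mortality matches ibrutinib monotherapy, and 11% or 22% at assumed related-death rates of 1% or 2%. The conclusion rests on accrual of about one subject a month, a constant hazard, independent subjects, and the absence of a death trigger in institutional policy that is not shown. Confidence is medium because of that last assumption and because the combination's related-death rate is unknown.

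**What to change.** Keep the 5-of-12 rule and the hold at the 12th subject, and add to Section 22:

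*Any death during study treatment or within 30 days of the last dose, while accrual is open, that the investigator considers at least possibly related to daratumumab or ibrutinib will be reported promptly to the DSMB, and enrolment will pause until the DSMB has completed an expedited review and recommends resuming.*

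The 30 days match the adverse event window in the synopsis. The relatedness bar is lower than in the stopping rule because a pause is reversible. No automatic termination is set. If institutional policy already provides this, cite it in Section 22 instead.

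The change uses the existing DSMB and serious adverse event reports. Its downside is an occasional pause, at about one subject of accrual per month. The plan gives no length for an expedited review; its one review hold, of about 3 months, includes observing the last subject through induction. The all-cause ceiling on firing is about 4% over the first 12 inductions, 11% to 13% up to the hold and 39% to 45% over full accrual, and lower once limited to related deaths. If the full-accrual figure is too high, the sponsor may limit the mandatory pause to the period before the 12th-subject review and require prompt DSMB review alone afterwards.
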